In the studies performed to-date, an increase in the precursor to aldosterone, 11-deoxycorticosterone (DOC) has been observed. DOC is also a potent mineralocorticoid which may replace aldosterone on its receptor. The levels of DOC were further increased at doses that inhibited cortisol, presumably driven by the rise in ACTH. In patients with already elevated levels of ACTH, combination with aldosterone blockade may lead to high levels of 11-DOC which could increase BP, decrease potassium, and cause fluid retention.

Preliminary data from this PoC study in CD patients (using doses higher than those tested in the hypertension studies) showed a tendency for decreases in mean systolic and diastolic blood pressure although the sample size is too small to make an appropriate estimate of the effect. During the extended treatment period introduced by [Amendment 4](#), patients will be re-educated on signs and symptoms of hypotension/ hypertension and BP will be monitored throughout the study.

Effects on the serum electrolytes

Blockade of aldosterone may physiologically increase potassium levels (hyperkalemia) and reduce sodium levels (hyponatremia). While reports of these abnormal laboratory parameters have generally been infrequent, transient, and mild in the studies conducted to-date with LCI699, serum electrolytes will be monitored closely. In addition, inclusion/exclusion criteria for baseline sodium and potassium levels will be strictly enforced.

Furthermore, levels of DOC might further increase at doses of LCI699 that inhibit cortisol, presumably driven by the rise in ACTH. In patients with already elevated levels of ACTH (i.e. Cushing's disease) combination with aldosterone blockade may lead to high levels of DOC which could lower blood potassium.

Preliminary data from the PoC study in Cushing's disease patients showed the following out of range potassium levels: 3 subjects had potassium levels < 3.5 mmol/L whereas 2 subjects had potassium levels > 5.3 mmol/L. Minimal or no changes were observed in plasma sodium.

Serum electrolytes will continue to be closely monitored during the extended study protocol.

Effects on adrenal hormones

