6. Fertile males, defined as all males physiologically capable of conceiving offspring **UNLESS** they use a condom during intercourse while taking the study medication and for 1 week after stopping study medication and should not father a child in this period. A condom is required to be used also by vasectomized men in order to prevent delivery of the drug via seminal fluid.
7. Patients who have been treated with mitotane during the last 6 months prior to Visit 1.
8. Patients with compression of the optic chiasm, in order to exclude patients with a tumor causing chiasmatal compression requiring surgery.

9. Patients who have a known inherited syndrome as the cause for hormone over secretion (i.e. Carney Complex, McCune-Albright syndrome, MEN-1, AIP).
10. Patients with Cushing's syndrome due to ectopic ACTH secretion or adrenal Cushing's syndrome.
11. Patients with pseudo-Cushing's syndrome (for patients with a mean UFC < 3xULN further testing to rule out this condition will be required unless Cushing's disease is confirmed by histopathology.) At least 2 of 3 tests should be abnormal in order to exclude pseudo-Cushing's: low-dose dexamethasone suppression test, dexamethasone-CRH test or late salivary or serum cortisol.
12. Patients with renal impairment (estimated creatinine clearance < 60 ml/min by the MDRD formula), serum creatinine >2.0 X ULN.
13. Patients who are not biochemically euthyroid.
14. Patients who have undergone major surgery within 1 month prior to screening.
15. Diabetic patients with poorly controlled diabetes as evidenced by HbA_{1c} > 9 %.
16. Patients who have congestive heart failure (NYHA Class III or IV), unstable angina, sustained ventricular tachycardia, clinically significant bradycardia, advanced heart block, history of acute MI less than one year prior to study entry or clinically significant impairment in cardiovascular function.
17. Patients with liver disease such as cirrhosis, chronic active hepatitis, or chronic persistent hepatitis, or patients with ALT/AST more than 3 X ULN, serum bilirubin >2.0 X ULN.
18. Patients who have any current or prior medical condition that can interfere with the conduct of the study or the evaluation of its results in the opinion of the investigator or the sponsor's medical monitor.
19. Patients who have a history of alcohol or drug abuse in the 6 month period prior to treatment.

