20. Patients with a history of non-compliance to medical regimens or who are considered potentially unreliable or will be unable to complete the entire study.
21. Patients who have received pituitary irradiation within five years prior to Visit 1.
22. Patients with risk factors for QTc prolongation or Torsade de Pointes, i.e. patients with a baseline QTcF > 470ms, hypokalemia, hyperkalemia, hypocalcaemia, hypomagnesaemia, uncontrolled hypothyroidism, personal or family history of long QT syndrome, or concomitant medications known to prolong the QT interval.

[figure not shown]
No additional exclusions may be applied by the investigator, in order to ensure that the study population will be representative of all eligible patients.

5 Treatment

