5.5.5 Dose modification and dose delay

For patients who do not tolerate the protocol-specified dosing schedule, dose adjustments are permitted in order to allow the patient to continue the study treatment. Instructions for monitoring liver function, and the criteria for withholding, re-initiating, reducing dose, or discontinuing study treatment are provided in [Table 5-1](#) below.

Table 5-1 Criteria for interruption and re-initiation of LCI699 for abnormal liver function

Isolated total Bilirubin elevation	
> ULN – 1.5 x ULN > 1.5 - 3.0 x ULN	Maintain dose level Interrupt study drug dose. Monitor liver function tests (LFTs) ^a , or more frequently if clinically indicated, until resolved to ≤ 1.5 x ULN: If resolved in ≤ 14 days, restart study drug and maintain dose level If resolved in > 14 days, then restart study drug and decrease by one dose level
> 3.0 - 10.0 x ULN*	Interrupt study drug. Monitor LFTs ^a weekly, or more frequently if clinically indicated, until resolved to ≤ 1.5 x ULN: If resolved in ≤ 14 days, then restart study drug and decrease by one dose level If resolved in > 14 days, then discontinue patient from study drug treatment. The patient should be monitored weekly (including LFTs ^a), or more frequently if clinically indicated, until total bilirubin has resolved to baseline or stabilized over 4 weeks.
> 10.0 x ULN*	Discontinue patient from study drug treatment The patient should be monitored weekly (including LFTs ^a), or more frequently if clinically indicated, until total bilirubin has resolved to baseline or stabilized over 4 weeks.
Isolated AST or ALT elevation	
> ULN - 3.0 x ULN > 3.0 - 5.0 x ULN	Maintain dose level Maintain dose level. Repeat LFTs ^a as soon as possible, preferably within 48-72 hours from awareness of the abnormal results; if abnormal lab values are confirmed upon the repeat test, then monitor LFTs ^a weekly, or more frequently if clinically indicated, until resolved to ≤ 3.0 x ULN
> 5.0 - 10.0 x ULN	Interrupt study drug. Repeat LFTs ^a as soon as possible, preferably within 48-72 hours from awareness of the abnormal results; monitor LFTs ^a weekly or more frequently if clinically indicated, until resolved to ≤ 3.0 x ULN. Then: If resolved in ≤ 14 days, restart study drug and maintain dose level If resolved in > 14 days, restart study drug and decrease dose by one level If not resolved after 4 weeks, discontinue patient from study drug.

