5.5.11 Discontinuation of study treatment

Patients may voluntarily discontinue from the study treatment for any reason at any time. If a patient decides to discontinue from the study treatment, the investigator should make a reasonable effort (e.g. telephone, email, letter) to determine the primary reason for this decision and record this information in the patient's chart and on the appropriate CRF pages. They may be considered withdrawn if they state an intention to withdraw, fail to return for visits, or become lost to follow-up for any other reason.

The investigator should discontinue study treatment for a given patient if he/she believes that continuation would be detrimental to the patient's well-being.

Study treatment must be discontinued under the following circumstances and according to Investigator discretion:

- Withdrawal of informed consent.
- Emergence of the following adverse events (compound specific):
 - hypertension defined as office mean sitting systolic BP > 180 mmHg or mean sitting diastolic BP > 110 mmHg (confirmed and persistent*).
- Any of the following laboratory abnormalities:
 - hyperkalemia (serum potassium > 5.5 mmol/L; confirmed and persistent*).
 - hypokalemia (serum potassium < 3.5 mmol/L; confirmed and persistent*).
 - hyponatremia (serum sodium < 130 mmol/L; confirmed and persistent*).
- QTcF > 500 msec, if confirmed by a cardiologist (see [Section 6.6.5](#)).
- QTcF > 480 msec, if the investigator determines it is no longer safe for the patient to continue in the study, based on ECGs, cardiac examination, and recommendation from a cardiologist (see [Section 6.6.5](#)).
- Pregnancy.
- Use of any other therapy for Cushing's disease.
- Any other protocol deviation that results in a significant risk to the patient's safety.

* Persistent is defined as unresolved with LCI699 dose or other concomitant medication changes

Patients who discontinue study treatment should NOT be considered withdrawn from the study. They should return for the assessments indicated in [Section 6](#). If they fail to return to return for these assessments for unknown reasons, reasonable effort (e.g. telephone, email, letter) should be made to contact them as specified in [Section 5.5.13](#).

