6.6.2 Vital signs

Vital signs include body temperature, BP and pulse measurements. After the patient has been sitting for 3 minutes, with back supported and both feet placed on the floor, systolic and diastolic blood pressure will be measured three times using an automated validated device, with an appropriately sized cuff. In case the cuff sizes available are not large enough for the patient's arm circumference, a sphygmomanometer with an appropriately sized cuff may be used.

Body temperature will be measured at visits according to the [Assessment schedules](#). Blood pressure and pulse rate will be measured at visits according to the Assessment schedules. If

vital signs are out-of-range at screening or baseline, the Investigator should obtain two additional readings, so that a total of five (5) consecutive assessments are made, with the patient seated quietly for approximately five (5) minutes preceding each repeat assessment. **At least the last reading must be within the ranges provided above in order for the patient to qualify.**

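### Exclusion 17 accepts a bilirubin band in which Table 5-1 interrupts LCI699 with no reachable restart; the sodium criterion and vital-sign ranges cited in Sections 3.5 and 6.6.2 do not exist

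*Protocol*

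**What the plan says.** **Bilirubin.** Exclusion 17 (Protocol Section 4.2, same limits in the synopsis) rules out "or patients with ALT/AST more than 3 X ULN, serum bilirubin >2.0 X ULN". Table 5-1 in Section 5.5.5 opens its isolated-bilirubin part with the bands "> ULN – 1.5 x ULN > 1.5 - 3.0 x ULN" and, in the same order, the actions "Maintain dose level Interrupt study drug dose". The lower band is therefore maintained and the higher one interrupted. Restart in the higher band requires resolution to 1.5 x ULN or below. Resolution within 14 days leads to the same dose level, and later resolution to one level lower.

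**Sodium.** Under serum electrolytes, Section 3.5 says that "inclusion/exclusion criteria for baseline sodium and potassium levels will be strictly enforced". Section 5.5.11 lists "hyponatremia (serum sodium < 130 mmol/L", confirmed and persistent, among the reasons to stop treatment.

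**Vital signs.** Section 6.6.2 provides for repeat readings when a screening or baseline value is out of range, then states: "At least the last reading must be within the ranges provided above in order for the patient to qualify". Section 5.5.11 lists mean sitting systolic pressure above 180 mmHg or diastolic above 110 mmHg, confirmed and persistent, as a reason to stop.

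**Site discretion.** Section 4.2 closes with "No additional exclusions may be applied by the investigator", and Section 4 says the same.

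**The concern.** An entry limit and an on-treatment action limit for the same test should fit together. Otherwise, an eligible patient can be taken off drug for a value that the protocol accepted at the start, and the record will look like a drug-related liver action. The SAP would carry this into the results. Under SAP Section 7.3.2.1 a missing mean UFC counts as non-response, and so does every time point after a non-administrative discontinuation. A UFC collected during an interruption enters the by-visit results as an off-drug value. SAP Section 7.5.2 also counts worst post-baseline laboratory grades whatever the baseline was. The planned shift tables show baseline values but do not connect them to an interruption or a stop.

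The sodium and vital-sign statements raise a different problem. Section 3.5 presents an entry criterion as a risk control, and Section 6.6.2 makes entry depend on ranges. If neither exists, sites cannot apply them, and a reader of the risk section is told of a control that is absent.

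**Working it through.** The plan gives no figure to reproduce. The check sets each entry limit against the matching action limit.

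| Parameter | Accepted at entry (4.2) | Action value | Overlap |
|---|---|---|---|
| Total bilirubin | up to 2.0 x ULN | interrupt > 1.5 to 3.0 x ULN (Table 5-1) | > 1.5 to 2.0 x ULN |
| ALT/AST | up to 3 x ULN | first interruption > 5.0 x ULN (Table 5-1) | none |
| QTcF | up to 470 ms | Day 1 discontinuation > 480 ms (6.6.5) | none |
| Potassium | hypo- and hyperkalemia excluded by name, no number | < 3.5 or > 5.5 mmol/L (5.5.11) | none by name |
| Sodium | no criterion | < 130 mmol/L (5.5.11) | number not barred |
| Blood pressure | no range | > 180 or > 110 mmHg (5.5.11) | number not barred |

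**Bilirubin, step by step.** Let b be total bilirubin in multiples of ULN.

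- Accepted: b ≤ 2.0. Interrupted: 1.5 < b ≤ 3.0. Both hold for 1.5 < b ≤ 2.0.
- Restart needs b ≤ 1.5, which no value in that band satisfies. A steady 1.8 is accepted (1.8 ≤ 2.0), interrupted (1.8 > 1.5) and never restarted (1.8 is not ≤ 1.5).
- Both the 14-day and the later restart branches presuppose resolution. The row states no outcome for a value that stays where it is.
- Table 5-1 adjusts for an elevated baseline in its combined AST/ALT-bilirubin row, as does Section 5.5.6. The isolated-bilirubin rows do not.
- The note allowing continued treatment for a purely indirect elevation applies only above 3.0 x ULN. An indirect value of 1.8 x ULN therefore lacks a route that a higher value has.

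**Sodium and vital signs.** Exclusion 22 names potassium, calcium and magnesium disorders. None of the inclusion criteria or the 22 exclusions mentions sodium. Section 6.6.2 describes how to measure but gives no range, and none appears in Sections 4.1, 4.2 or the synopsis. No blacked-out text is marked in 6.6.2.

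**Timing.** The Amendment 6 rationale reports 19 patients enrolled by 01 March 2014, with 17 having completed the core phase and 2 discontinued. Since 17 + 2 = 19, no patient remained in the core phase. The SAP dates Amendment 7, which brought in Table 5-1, to 17 February 2016. Twelve patients were then still in the long-term extension (count as of 30 November 2015).

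**Weight of a patient.** The documents do not say how many patients are affected. If k of the 12 ongoing patients were, the share would be k/12: 0 for k = 0, 8.3% for k = 1, and 16.7% for k = 2. The values of k are assumptions. The SAP denominator at extension visits also keeps earlier non-administrative discontinuations. Against the 16 who entered extension-1, one patient is 1/16 = 6.3 percentage points.

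**The case against.** **The stopping rules.** A reader might infer that the protocol admits patients who already meet its stopping rules. The documents do not support that. The sodium and blood pressure rules in Section 5.5.11 need a confirmed value that persists after changes to LCI699 or other medication, and they are subject to investigator discretion. Hypertension is listed there as an emerging adverse event, and under Section 7.1 a condition present before consent counts as one only if it worsens. A baseline value alone does not meet these rules. Only the bilirubin row acts on an unchanged entry value.

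**Other safeguards.** Nor does it follow that sites must take any patient with an abnormal sodium or blood pressure. Section 6.6.4 requires the investigator to judge and document any baseline laboratory result outside the reference range where the protocol gives no range, and this covers sodium. Exclusion 16 covers clinically significant cardiovascular impairment, and exclusion 18 any interfering condition. Exclusion 22 does bar hypo- and hyperkalemia, and electrolytes are monitored throughout. These points stand. They provide case-by-case judgement, though, not the enforced criterion or the ranges that Sections 3.5 and 6.6.2 describe.

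**Timing.** No patient was screened while exclusion 17 and Table 5-1 were both in force, and for extension patients the current bilirubin matters more than the entry value. This also stands and confines the effect. It does not remove it: the table governs continued treatment of patients accepted under the 2.0 x ULN limit.

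**Efficacy.** Harm to the main efficacy results is another tempting inference. Table 5-1 came after the Week 10 and Week 22 visits, and the SAP says both analyses are already reported. Interruption alone does not make a patient a non-responder; a missing or uncontrolled mean UFC, or a discontinuation, does.

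**Conclusion.** The point holds in three parts. First, total bilirubin above 1.5 and up to 2.0 x ULN is both accepted by exclusion 17 and an interruption value in Table 5-1, with no baseline adjustment and no reachable restart while the value is unchanged. ALT/AST and QTcF show no such overlap, and potassium shows none by name. Second, the sodium criterion cited in Section 3.5 is not in Sections 4.1 or 4.2. Third, the ranges on which Section 6.6.2 makes qualification depend are not given.

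The practical size is limited. The bilirubin conflict can affect only extension visits, and only a patient whose bilirubin is still in that band. The documents show no such patient. The figures of 8.3 and 6.3 percentage points are the weight of one patient, not estimated effects. The conclusion assumes that the isolated-bilirubin rows are applied as written. It is worth correcting because the remedy is small and the long-term extension results rest on few patients; it does not put the primary result in doubt.

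**What to change.** Reconcile exclusion 17 with the isolated-bilirubin rows of Table 5-1. Which passage changes is the sponsor's decision, and no limit is proposed here. Reconcile the statements in Sections 3.5 and 6.6.2 with the eligibility criteria actually in Sections 4.1 and 4.2. Enrolment is complete, so this corrects the record and the rules for patients still treated; it cannot change who entered.

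In the Final CSR, flag every patient whose baseline bilirubin, sodium or blood pressure already lay beyond a Table 5-1 or Section 5.5.11 value. Show interruptions and discontinuations with and without those patients. If there are none, say so.

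The cost is protocol wording and one extra flagged listing from data already collected.

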5.1 Investigational treatment

The investigational drug, LCI699 1 mg and 5 mg capsules, will be prepared by Novartis and supplied to the Investigator as open labeled bulk medication.

In addition, LCI699 open labeled 1mg, 5mg, 10mg and 20mg tablets will be prepared by Novartis and supplied to the Investigator.

5.2 Treatment arms

This study has only one treatment arm; LCI699. Patients will start on a dose of 2 mg b.i.d. if baseline mUFC is $\leq 3x$ ULN or 5 mg b.i.d. if baseline mUFC is $> 3x$ ULN and increase their dose every 2 weeks as illustrated in [Figure 3-1](#) up until week 10. From week 10 to week 22, the dose will be adjusted as needed based on efficacy and tolerability.

5.3 Treatment assignment

Treatment numbers will be assigned in ascending, sequential order to eligible patients in accordance with entry into the study. The treatment number becomes the definitive subject number as soon as a patient receives the first dose of the respective study treatment.

5.4 Treatment blinding

Not applicable as this study is open label.

5.5 Treating the patient

5.5.1 Patient numbering

[figure not shown]
Screening number

Each patient screened is assigned a unique screening number. The screening number is a combination of the center number, which is provided by Novartis, and a three digit number starting with [REDACTED] for each patient which is assigned by the Investigator. Therefore, if the center number is [REDACTED] (any leading zeros in the center number are dropped) the screening numbers will be assigned such as [REDACTED] in ascending order. If the center number is [REDACTED] the screening numbers will be [REDACTED] in an ascending order.

Starting with [Amendment 4](#) each patient will be identified in the study by a Patient Number (Patient No.) which is assigned when the patient is first enrolled for screening and is retained as the primary identifier for the patient throughout his/her entire participation in the study. The Patient No. consists of the Site Number (Center No.) (as assigned by Novartis to the investigative site) and patient number suffixed to it, so that each patient is numbered uniquely across the entire database. Upon signing the informed consent form, the patient is assigned to the next sequential Patient No. available to the investigator. Patients that previously completed Part I and reenter the study for Part II (core PoC follow-up cohort) are to be assigned a new patient number. A record of the old screening number and the new patient number is to be kept. If a patient is rescreened after being screen failed, then a new patient number is to be used. With [Amendment 4](#), the patient number will also be captured on the eCRF.

Treatment number

If the patient is deemed eligible for enrollment into the study and will commence dosing, a treatment number will be assigned. Treatment numbers will be assigned in ascending, sequential order to eligible patients in accordance with entry into the study. The treatment number becomes the definitive subject number as soon as a patient receives the first dose of

the respective study treatment. Patients that previously completed the study and reenter the study after [Amendment 4](#) (core PoC follow-up cohort) are to be assigned a new patient number. A record of the old treatment number and the new patient number is to be kept.

Once assigned to a patient, a treatment number will not be reused.

There should be a source document maintained at the site which links the screening number to the treatment assignment number (once assigned).

Patients will be assigned treatment numbers; each site will have a list of unique treatment numbers.

5.5.2 Dispensing the study treatment

Appropriate documentation of the patient specific dispensing process must be maintained.

Bulk medication labels will be in the local language, will comply with the legal requirements of each country, and will include storage conditions for the drug but no information about the patient.

